By necessity, clinical research coordinators administering the consent process in both parent trials are unmasked to the incentive information being messaged to prospective participants. The introduction to the study and the informed consent process have been robustly scripted for research staff involved in both trials to ensure that messaging is consistent and biases are minimized.

4. Population

Eligibility for RETAIN is contingent on eligibility for the BASC and MOVE IT parent trials.

- Adults age 18 years or older who are daily smokers with current or lifetime major depressive disorder without psychotic features (BASC)
- Adults age 18 years or older who are admitted for inpatient care to the Hospital of the University of Pennsylvania (HUP) on medicine or oncology floors (MOVE IT)

Patients randomized to RETAIN must be:

- Eligible for parent RCT
- 18 years or older
- English-speaking

In the BASC trial, prior knowledge of the incentive randomization or payment equalization used for this study, which will be assessed with open-ended prompts during the first encounter, is an exclusion criterion. We will not assess for prior knowledge in the inpatient MOVE IT study population. However, only one patient per hospital room will be approached for the MOVE IT study to protect against contamination.

5. Primary outcome and analytic method

a. Primary outcome

The primary outcome is the proportion of participants assigned to each incentive amount that consent to enroll in each of the two parent RCTs.

b. Primary analytic sample

Intention-to-treat (ITT) approach such that the analytic sample will include all patients randomized in the RETAIN trial, even if ultimately deemed ineligibile for the parent trials.

c. Primary analysis

We will first assess bivariate relationships of incentives with the primary outcome using chi-square tests for comparisons of proportions. To examine the hypothesized statistical interactions, we will use logistic, linear, or quantile regression, as appropriate based on outcome parameterizations and distributions. For all outcomes other than tests for undue or unjust inducement, we will adjust significance levels for multiple comparisons using the Holm method.

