Interim analyses will be performed by the trial's primary statistician who will conduct all analyses blinded to trial arm. Investigators, the project manager, and the DSMB will remain blinded to treatment arm through completion of analyses. The data manager and faculty statistician have been unblinded as was necessary to perform essential functions of their roles.

.						
Date	Change	Reason for change				
1/27/2020	We realized that because the incentive arm was to be treated as an ordered variable, per the chi-squared test, there was no role for 'Holm' adjustment for multiple testing as this was a single test.	The incentives are in increasing order and tests with an ordered variable have only a single contrast, obviating the need for adjustment.				
1/27/2020	Use of Jonckheere- Terpstra test instead of Kruskal-Wallis.	To make comparisons across ordered incentive groups, the Jonckheere test is the appropriate statistic for non-parametric data, rather than the Kruskal Wallis.				
1/27/2020	We implemented a diagnostic check to detect outlier and influential observations.	The compared riskiness data were observed to be very sparse in the higher-risk ranges, particularly in the Ambulation trial. This diagnostic was designed to ensure that inferences were not driven by a few influential observations.				
1/27/2020	Given extremely limited RETAIN secondary outcome data among patients who do not consent to the parent trials, we will analyze secondary outcomes among consenting subjects only.	Very few patients who chose not to consent to the parent trial were willing to complete these post-consent instruments, so there was no basis for including non-consenting patients in tests of secondary outcomes. Instead, we limit our contrasts to those among incentive arms among the consenting patients.				

V. Changes to Statistical Analysis Plan

4 /27 /2222		
1/2//2020	Secondary	These outcomes are analyzed among the consented sample
	outcomes were	because of aforementioned limitations in capturing secondary
	analyzed 2 ways	outcomes. Participants who consented and didn't consent might be
	for both trials:	different and non-response might not be at random. To check if the
	Primary	inference is robust we planned for both analyses.
	approach-	
	Unweighted;	
	Secondary	
	approach –	
	adjusted for	
	response rate	
	using propensity	
	weights.	
2/17/2020	Included	During the interim analyses we gained meaningful insight into the

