The primary outcome is the proportion of participants assigned to each incentive amount that consent to enroll in each of the two parent RCTs.

b. Primary analytic sample

Intention-to-treat (ITT) approach such that the analytic sample will include all patients randomized in the RETAIN trial, even if ultimately deemed ineligible for the parent trials.

c. Primary analysis

We will first assess bivariate relationships of incentives with the primary outcome using chi-square tests for comparisons of proportions. To examine the hypothesized statistical interactions, we will use logistic, linear, or quantile regression, as appropriate based on outcome parameterizations and distributions. In the above analyses we treated incentive as an ordered variable. In all analyses in which the parent trial enrolls in multiple centers, we will model the center from which patients are recruited as a fixed effect, thereby mitigating confounding by center and adjusting variance estimates for clustering of participants within centers. To adjust for chance covariate imbalance among arms, primary analyses will include covariates (see Table 1) in multivariable models if they are significantly associated with the intervention arm and predictive of enrollment in the parent trials in bivariate analyses. To avoid problems in estimating odds ratios due to sparse data, we will limit the number of covariates to no more than 1 per 10 participants enrolling in the parent trials. In all analyses related to the BASC parent trial, we will model the center from which patients are recruited as a fixed effect, thereby mitigating confounding by centers are recruited as a fixed effect, thereby mitigating confounding by center and adjust related to the BASC parent trial, we will model the center from which patients are recruited as a fixed effect, thereby mitigating confounding by center and adjusting variance estimates for clustering of participants within centers.

Our analyses to rule out undue and unjust inducements entail three primary covariates: risk perception, annual household income, and economic well-being. All models will use enrollment in the parent trial as the outcome. To determine if incentives represent undue inducements for research participation, we will test the statistical interaction between incentive size and the primary covariate of risk perception on

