the outcome of enrollment in the parent trials. We will test two interactions, each in a separate model to avoid collinearity, to determine if incentives represent unjust inducements: that between incentive size and the primary covariate of annual household income, and that between incentive size and the primary covariate of economic well-being. All analyses will be stratified by parent study.

Analyses of interaction terms will be structured as tests of non-inferiority. The null hypothesis, for both trials, will be that the use of incentives meets criteria for undue or unjust inducement. We can reject the null, and conclude the absence of undue or unjust inducement, if the interaction terms are "small" according to pre-specified criteria (in technical terms, the inferiority margin). Said a different way, our analyses are designed to determine if we can exclude the possibility that incentives represent undue or unjust inducements if the resulting interaction terms are sufficiently small. Specifically, we will use one-sided alpha levels of 0.05 to exclude, with 95% confidence, the possibility that any of these interaction odds ratios are >2.0.

We will explore temporal trends in incentives' effects over the study period using stratified analyses. If temporal trends are noted, as may occur if prospective patients learn of the incentives used in these studies, we will adjust for their influence by entering time as a covariate, modeled as a spline. We will evaluate potential effect modifiers (variables in Table 1) using stratified analyses. If differences among strata appear, we will formally test their corresponding interactions with the incentive amount.

TABLE 1 FACTORS FOR ADJUSTMENT AND EXPLORATION OF EFFECT MODIFICATION

Potential factors for adjustment			
Patient level covariates	Variable coding or definition		
• Age	Continuous		
• Gender	Binary		
• Race	Categorical		
Marital status	Categorical		
Education	Categorical		
Income	Categorical		
Economic well-being	Categorical		
Prior research participation	Categorical		
Attitudes towards research:	Continuous, measured using the Research Attitudes Questionnaire-7 (RAQ- 7).		

6. Secondary analysis

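### The Final SAP tests effect modifiers only once strata look different, with no threshold, alpha or stated count, and leaves RAQ-7 to the same rule

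*Combined protocol and SAP*

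**What the plan says.** The rule is in the Final SAP, section 5.c (Primary analysis), and has two steps. First: "We will evaluate potential effect modifiers (variables in Table 1) using stratified analyses". Then: "If differences among strata appear, we will formally test their corresponding interactions with the incentive amount".

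The table is headed "TABLE 1 FACTORS FOR ADJUSTMENT AND EXPLORATION OF EFFECT MODIFICATION". It lists nine factors: age, gender, race, marital status, education, income, economic well-being, prior research participation and RAQ-7. The two trials are handled apart: "All analyses will be stratified by parent study". On the form of the exposure, the section says "In the above analyses we treated incentive as an ordered variable".

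The only significance level given in 5.c belongs to the non-inferiority tests: "we will use one-sided alpha levels of 0.05 to exclude, with 95% confidence". For the modifier tests the section gives no alpha, no definition of an apparent difference, no cut points for stratifying age or RAQ-7, and no instruction to state how many factors were looked at.

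Three of the nine factors have an interaction with incentive set out elsewhere, whatever the strata show:
- Income and economic well-being are primary covariates in 5.c, each with a non-inferiority test against an interaction odds ratio of 2.0.
- RAQ-7 is item 1 in section 3.c of the Final Protocol. It is measured before the incentive is disclosed, partly to see whether incentives modify its relation to enrolling. The protocol says that such modification would point to undue inducement. In the Final SAP, RAQ-7 appears only in Table 1.

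**The concern.** A test that is run only because the same data already look different does not have its nominal error rate. The factors most likely to be picked out are those on which chance has produced a difference, so the p-values that get reported come from a selected set. Without a threshold the selection cannot be reproduced, and without a stated count a reader cannot judge how surprising one positive result is.

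The matter is most pointed for RAQ-7. The protocol gives that interaction an ethical meaning, but the SAP would test it only if the strata suggest it. If they do not, the protocol's assessment has no planned formal result. If they do, the result comes from a screened test.

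**Working it through.** The plan states no error rate for the modifier tests, so there is no figure of its own to reproduce.

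**Inputs from the documents.** Nine factors (Table 1); two trials analysed separately (5.c); incentive ordered, which I take to mean one incentive contrast per factor. Removing income and economic well-being (5.c) and RAQ-7 (Final Protocol 3.c) leaves 9 − 3 = 6 factors with no interaction specified elsewhere.

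**Assumptions.** Two-sided alpha 0.05 per test; one overall test per factor, including the multi-category ones; no true modifiers; the look and the test rest on the same statistic; thresholds for the look of |z|>0.5 and |z|>1; correlation between test statistics of 0 to 0.5.

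**Step 1: effect of the look on the tests that are run.** For a null factor and a threshold s below 1.96,

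P(p<0.05 given tested) = 0.05 / P(|Z|>s).

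- s = 0.5: 0.05 / 0.617 = 0.081, about 8%.
- s = 1: 0.05 / 0.317 = 0.158, about 16%.

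**Step 2: does the look raise the overall chance of a false positive?** No. Any factor with |z|>1.96 passes every look with a lower threshold, so the chance of at least one significant result is the same as if all factors were tested. That chance comes from the number of factors. The look affects how the reported p-values should be read.

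**Step 3: chance of at least one significant modifier.** Under independence this is 1 − 0.95^k for k tests.

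| Factors | One trial | At least one of two trials |
|---|---|---|
| Six others | 1 − 0.95^6 = 26.5% | 1 − 0.95^12 = 46.0% |
| All nine | 1 − 0.95^9 = 37.0% | 1 − 0.95^18 = 60.3% |

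With nine equally correlated statistics (simulation, 400,000 draws), rho 0.3 gives 32.6% and 54.6%, and rho 0.5 gives 26.9% and 46.6%. Positive correlation lowers the figures, so the six-factor results are upper values at this alpha.

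**Step 4: sensitivity to the assumed alpha.** At two-sided 0.10 under independence, six factors give 46.9% and 71.8%, and nine give 61.3% and 85.0%.

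**The case against.** The strongest reply is that the plan already signals the status of this work. The table title speaks of exploration and the text of potential modifiers. A formal test may simply mean fitting an interaction term instead of comparing subgroup p-values, which is good practice. No stopping rule, primary conclusion or sample size depends on the result. A reader who looks for the same factor, in the same direction, in both trials would seldom be misled: for nine independent null factors that chance is 1 − (1 − 0.05 × 0.025)^9 = 1.1%. All of this stands, and it keeps the point small. It does not supply a threshold, an alpha or a count, and it does not settle RAQ-7.

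Four stronger readings are tempting, and the documents do not support them:
- *A spurious modifier is likely.* Within one trial the chance is at most 37% at the assumed 0.05. Over both trials it passes one half for all nine factors only when correlation is low, and for the six other factors it does not.
- *Dropping Holm removed the protection.* The Original SAP sentence reads "For all outcomes other than tests for undue or unjust inducement, we will adjust significance levels for multiple comparisons using the Holm method". It concerns outcomes, not modifiers of one outcome. The change log's reason, "there was no role for 'Holm' adjustment for multiple testing as this was a single test", concerns the ordered-arm comparison. Neither clearly covered modifiers.
- *Factors that do not look different will go unreported.* The SAP says all Table 1 variables will be evaluated and nowhere says that results will be withheld. It only fails to require the count.
- *A chance finding for race, gender, age or education would count as inducement.* The SAP ties inducement to risk perception, income and economic well-being. Among the other Table 1 factors, only RAQ-7 is given that meaning, and that is in the protocol.

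**Conclusion.** The point holds as a minor one. The look-then-test rule makes the p-values of the tests that are run anti-conservative: about 8% to 16% of tested null factors reach p<0.05 at the two thresholds assumed. With no true modifiers, the chance of at least one significant result is up to 27% per trial and 46% over both for the six factors not specified elsewhere. For all nine it is 27–37% per trial and 47–60% over both (rho 0.5 to 0). These figures rest on a two-sided 0.05 and on correlations that the documents do not give. RAQ-7 is the clearest gap, because a protocol-level assessment has been left to a data-triggered test. The primary enrollment comparison, the three inducement tests and the sample size are unaffected.

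**What to change.** In Final SAP 5.c:
- Delete the conditional trigger. In each trial, fit and report the incentive interaction for every Table 1 factor that is not a primary covariate, with estimates and confidence intervals.
- Keep age and RAQ-7 continuous.
- State the number of interactions examined and call the results hypothesis-generating.
- Leave income and economic well-being to their primary tests.
- Specify the RAQ-7 interaction separately, as the assessment that the Final Protocol describes.

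Holm adjustment across factors within a trial is optional and a matter of preference for analyses of this kind.

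The cost is a change of wording and a few extra model fits on data already collected. The downside is that any single modifier will be read less favourably once the number examined is in view.

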All participants who are randomized and enrolled in RETAIN and consent to the BASC and MOVE IT will be debriefed on the randomization of incentives and the purpose of the RETAIN study will be explained (see Sections 8.g. and 8.h. Debriefing in BASC and MOVE IT, respectively).

d. Administration of Survey Instruments

i. BASC

Procedures for this study will commence during initial pre-screening eligibility assessment via phone for the BASC trial. During this call, all study candidates will complete an initial eligibility assessment with research staff members from the clinical site from which they are being recruited (Northwestern or Penn). Research staff will begin with the BASC eligibility screen survey, which includes basic demographic questions, as well as questions related to participants' endorsement of symptoms of clinical depression. Once a patient is determined to be preliminarily eligible for BASC, the research staff will ask the RETAIN eligibility prompt to assess for prior knowledge of the specific incentives or randomization used for RETAIN. Participants who do not have prior knowledge of the RETAIN incentives or randomization will be randomized by the research staff via the BASC trial's Data Management System (DMS) (see Section 10.a.1 Data Collection and Data Confidentiality – BASC). Prospective participants will then be introduced to BASC study basics and risks and informed that if they are determined to be eligible for the BASC study and participate in the BASC trial, they will receive \$0, \$200, or \$500 for participation.

Prospective participants who have prior knowledge of the incentives or randomization used for RETAIN will not be randomized, enrolled, or receive RETAIN-related messaging on the phone call. They will receive the standard study information regarding session and travel compensation for the BASC trial without RETAIN messaging. For information on remuneration in the BASC trial, see Section 6.d. These participants will not be debriefed or paid the RETAIN incentives.

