Before research staff finalize logistical details on the BASC study and schedule intakes for tentatively eligible patients, they will administer several RETAIN-related questionnaires to assess 1) demographics and personal financial well-being, 2) attitudes towards biomedical research, 3) prior experience in research, and 4) perceptions of research risk. The screener will administer these surveys via phone using CRF forms adopted for the RETAIN trial that will later be scanned into the BASC trial's DMS.

Participants who pass the BASC pre-screening will be scheduled to attend a 2-3½ hour Intake session for the BASC trial. During the intake session, BASC research staff at Penn and Northwestern will read a pre-BASC consent script before presenting an electronic image of the BASC informed consent/ HIPAA forms with additional information regarding the RETAIN incentive randomization condition; this electronic image will be presented via tablet or desktop. By presenting the BASC consent with randomized compensation information electronically, we will assess the amount of time participants spend reading each part of the main trial consent form. Each section (e.g., Study Introduction, Procedures by Visit, Possible Risks and Discomforts, etc.) will be presented as a survey in REDCap. Time-stamp data collected for this REDCap module will be linked by the study ID generated in the BASC Data Management System during candidates' telephone pre-screen call (see Section 10.a.1. Data Collection and Data Confidentiality - BASC).

Once participants finish reading and before signing a paper version of the BASC trial consent, they will complete brief assessments of perceptions of research risk (administered over the telephone pre-screen and again at intake – see Section 9.a. BASC Study Calendar). They will also complete assessments on perceptions of the difference between research and individualized patient care and understanding of the smoking cessation study via a trial elements quiz. All of these measures will be administered via the CRF paper and pencil processes currently used in the BASC trial. The responses to the quiz will be reviewed with participants, during which participants' questions will be answered.

ii. MOVE IT

Clinical research coordinators will identify patients through electronic health record-based screening for the MOVE IT study and preliminarily eligible patients will be approached for recruitment in their hospital rooms.

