	secondary	risk score distributions. We found that in the Ambulation trial the
	analysis of the	risk score mostly (>85%) clumped on 0, and in the smoking trial the
	risk score and	score is extremely right skewed. To better handle this sparsity of
	incentives where	data we planned a secondary analysis in which we treat the risk
	risk score is	scores as binary and compare the inferences.
	treated as a	
	binary variable (0	
	and >0).	

VI. Final Statiscal Analysis Plan

1. Background and rationale

This study is designed to provide the first-ever real-world tests of a broad range of intended and unintended consequences of financial incentives for research participation. It will do so through the conduct of two separate, but similarly designed, embedded randomized trials within actual parent clinical trials. It is our hope the findings from this study will inform research regulations and guide the use of incentives in future RCTs so as to expedite medical innovation and improve health

2. Objectives and hypotheses

The aims of this study are to (1) determine if the ethical concerns with incentives for research participation actually manifest; and (2) assess the possible scientific and ethical benefits of financial incentives for RCT participation.

We hypothesize that research incentives will:

- Augment participants' perceptions of risk without disproportionately encouraging economically disadvantaged participants to enroll
- Demonstrate an increased enrollment fraction in the parent trials, thereby enhancing the scientific value and validity of the research by augmenting the precision of the studies

3. Design and randomization

RETAIN comprises two prospective randomized controlled trials, embedded within two parent trials conducted in parallel, each comparing three intervention arms. Arms vary by the amount of the financial incentives that are offered to potential participants. Amounts offered differ on a per trial basis determined by the relative time and effort being asked of the participant for each parent trial. Assignment to arms is determined by computerized random-number generation with block randomization using variable block sizes of 3 and 6. Participants in both embedded trials have a 33.3% probability of being assigned to each RETAIN arm.

a. BASC Trial

• The Behavioral Activation and Varenicline for Smoking Cessation in Depressed Smokers Study (BASC) (NCT 02378714)

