We will implement secondary interaction analyses of risk score with incentive arm. Risk score will be treated as binary variable with 0 and >0 categories and Incentive will be treated as ordinal factor. The analysis method will be same as described in section **c**. We plan to compare the inference of this analysis with the primary approach and report accordingly.

a. Approach to outliers and influential observations

We plan to perform diagnostic checks for influential and outlier observations in interaction analyses. The analyses will be done both ways including and then excluding influential observations if any is detected. To implement the diagnostic process we will use 'car' package from R.

b. Secondary outcome measures

Attention to the informed consent document: We will assess the amount of time patients spend reading each part of the parent trial consent form by setting up each section as a "survey" in REDCap. The data extract will include the time – to the second – at which the participant moved to another section through a timestamp. The primary measure of this assessment will be time spent on the risk section; the secondary measure will be total time spent on the consent form.

Perceived risks of the research: Perceived risks of the research will be measured by a modified 9-item "compared riskiness" scale, which has been used in previous studies and refined for the RETAIN trial.

Incidence of therapeutic misconceptions: It has been hypothesized that the use of financial incentives could reduce therapeutic misconceptions, and thereby promote informed decision-making. Because patients are not accustomed to being paid for their clinical care, offering incentives could signal that research is different. We will test the hypothesized benefit of research incentives by measuring the incidence of therapeutic misconception in each incentive arm. We will assess this outcome with a 4-item therapeutic misconception tool, developed by External Advisory Board member, [name].

Understanding of the trial: To assess whether increased attention translates into improved understanding of the trial, we will use a 6-item Trial Elements Quiz, featuring core elements of the parent trials' consent forms.

Perceptions of influence or coercion: To measure general perception of coercion and voluntariness of research participation, we will use the five-item Perceived Coercion Scale of the MacArthur Admission Experience Survey.

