Retention through the end of treatment sessions: To assess the impact of incentives on retention status in the protocol, we will disburse payment in two installments- one as soon as possible after debriefing and one during the patient's last week of treatment therapy or study intervention. The denominator for analyses of this outcome will be all those who received the first payment. We will assess if patients completed their treatments is associated to incentive amounts.

c. Analysis of secondary outcomes

We will first test the bivariate relationships between incentives and secondary outcomes using ANOVA or Jonckheere-Terpstra test for normally and non-normally distributed continuous variables, and chi-square tests (trend tests) for comparisons of proportions. In all of these analyses the incentive arm was included as an ordered variable. All the secondary outcomes are assessed among participants who consented for the trials. Due to limited sample size we plan to perform the unadjusted analyses.

Participants who consented and who didn't might be different meaning non response might not be random. To check if the inference is robust or not we plan to analyze the appropriate secondary outcomes 2 ways- unweighted and weighted. In survey weighted approach we plan to use propensity scores (inverse of probability of consent) as weights.

7. Sample size and statistical power calculations

a. Sample size

We plan to enroll 576 patients who are approached for participation in each parent trial, such that the total RETAIN sample will include 1,152 patients. However, RETAIN data associated with each of the two
parent trials will be analyzed separately in primary analyses.

b. Statistical power calculations

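### Final SAP 6.c compares perceived risk by incentive arm only among consenters, although the scale precedes the consent decision, so incentives can appear to raise perceived risk when they do not

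*Combined protocol and SAP*

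**What the plan says.** - **Hypothesis.** Final SAP section 2 expects incentives to augment "perceptions of risk without disproportionately encouraging economically disadvantaged participants to enroll".
- **Outcome.** Section 6.b: "Perceived risks of the research will be measured by a modified 9-item" compared-riskiness scale. No time point is given.
- **Analysis set and test.** Section 6.c: "All the secondary outcomes are assessed among participants who consented for the trials". The comparison is unadjusted, with arm ordered (ANOVA or Jonckheere-Terpstra).
- **Reason.** The 1/27/2020 entry in the Changes to SAP opens "Given extremely limited RETAIN secondary outcome data among patients who do not consent to the parent trials" and explains: "Very few patients who chose not to consent to the parent trial were willing to complete these post-consent instruments".
- **Timing, BASC.** Final Protocol 8.d.i: after randomisation, "Prospective participants will then be introduced to BASC study basics and risks" and told the payment. The scale follows by phone. Later, after reading the consent form and before signing, "they will complete brief assessments of perceptions of research risk (administered over the telephone pre-screen and again at intake").
- **Timing, MOVE IT.** Final Protocol 8.d.ii places the scale after the consent form is read and before signing. Changes to Protocol 9.a (April 2018) reports adding it to the baseline surveys so that early decliners would have a score. Either placement precedes the decision.
- **Robustness analysis.** Section 6.c, for those secondary outcomes it considers appropriate: "In survey weighted approach we plan to use propensity scores (inverse of probability of consent) as weights". It names neither the outcomes nor the covariates of the consent model.

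**The concern.** Consent is the primary outcome, and section 2 of the Final SAP expects incentives to raise it. Restricting a comparison of arms to consenters therefore compares groups that are no longer the randomised ones. If higher perceived risk discourages enrolment and money encourages it, the high-incentive arm keeps more of its risk-averse members. Mean risk among consenters then rises with incentive even when no one's perception has moved. That is the direction of the first hypothesis, and it can hide a real fall in perceived risk.

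The logged reason does not describe this scale, which is not a post-consent instrument. The primary incentive-by-risk model in 5.c has enrolment as its outcome, so it already needs scores from people who decline.

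**Working it through.** **1. Inputs.** The plan gives no power or precision for this comparison. Its only power figure (section 7.b) concerns the interaction test, and this point does not rest on it.

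From the documents: 192 per arm and about 50% enrolment overall. The 2/17/2020 change entry says that more than 85% of MOVE IT scores are at zero and that BASC scores are extremely right skewed.

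Assumed, because the documents are silent:
- enrolment by arm of 35/50/65% or 40/50/60%;
- an odds ratio (OR) of enrolment per SD of risk of 0.5, 0.67 or 0.8;
- a BASC-like score that is geometric (p = 0.4) and truncated at 9;
- a MOVE IT-like score with 86% at zero and a geometric tail on 1-9.

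**2. Direction.** Let logit P(enrol) = a_arm + b·z, with z the standardised score. Among consenters in an arm with enrolment P, mean z shifts by Cov(z, p(z))/P, which for small b is about b(1 − P). With no true effect of incentive on risk,

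high minus low ≈ b_high(1 − P_high) − b_low(1 − P_low).

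- Common slope OR 0.8 (b = −0.223), 40% against 60%: −0.223 × 0.4 + 0.223 × 0.6 = +0.045 SD. The exact value for a normal score is 0.044.
- Slope 0: no shift. This is the planning value in section 7.b, which sets the risk OR to 1 at $0 and assumes a true interaction OR of 1.
- Slope OR 0.5 (b = −0.693) in the low arm and 0.8 in the high arm, 50% enrolment in both: 0.5 × (0.693 − 0.223) = +0.235 SD. The exact value for a BASC-like score is about 0.18. A flattening slope thus produces bias even without a difference in enrolment.

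**3. False rejection.** Simulation with no true effect, consenters only, two-sided 5% Jonckheere-type trend test:

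| OR per SD, by arm | BASC-like, 35/50/65% | BASC-like, 40/50/60% | MOVE IT-like, both gradients |
|---|---|---|---|
| 1 in all | 5% | 5% | 5% |
| 0.8 in all | 6-7% | 6% | 5-6% |
| 0.67 in all | 8-10% | 7% | 5-7% |
| 0.5 in all | 15-16% | 9-10% | 5-8% |
| 0.5/0.67/0.8 | about 36-43% (both gradients) | | about 24-25% (repeat runs 22-27%) |

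Using all randomised participants gives about 5% in every row. In the last row the spurious high-minus-low difference is +0.24 to +0.26 SD (BASC-like) and +0.14 to +0.15 SD (MOVE IT-like). That row is the pattern that Final Protocol 11.c treats as undue inducement: risk less strongly tied to enrolment at higher payment. The implied interaction OR is 0.8/0.5 = 1.6 per SD.

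**4. Masking.** With a true fall of 0.25 SD, a BASC-like score and a common slope of 0.5 to 0.8, consenters-only power is 8-29%. It is 39-41% if only the sample shrinks, and about 71% if everyone is scored.

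**5. The planned weights** (common OR 0.5, 35/50/65%). The bias is +0.11 SD unweighted, +0.11 with arm alone in the consent model, +0.10 with arm and a covariate correlated 0.3 with risk, and +0.02 with risk by arm. Only the last works, and fitting it needs decliners' scores.

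**6. How far the remedy goes.**
- If a random quarter of decliners have a score, false rejection is 5-6% under a common slope (BASC-like). Under the flattening slope it is about 16% (BASC-like) and 9% (MOVE IT-like) at 35/50/65%.
- If having a score itself depends on arm and risk (OR 0.5 at each stage, BASC-like), the all-scored test rejects 14% against 25% in consenters with 60/70/80% scored and 35/50/65% enrolled. With 75/80/85% scored it is 8% against 21%. There is no gain with 60/70/80% scored and 40/50/60% enrolled (14-15% each).
- In that setting the MOVE IT-like score shows little or no gain (7-9% against 7-11%).
- If the BASC outcome is the intake score (ORs 0.5/0.67/0.8 as separate common-slope cases, 60/70/80% attending, 35/50/65% signing), signers reject 20/11/6% and everyone at intake 9/7/5%.

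**The case against.** **The size is wholly assumed.** This stands. Under the plan's own planning values the bias is zero. Those values look like a power convenience, though. Final Protocol 12.a reports that higher stated risk lowered willingness to join hypothetical trials, and that the risk-by-payment interaction was not significant (p = 0.30). A negative slope is therefore plausible, and a common slope is not excluded.

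**The plan has partly dealt with it.** Section 6.c concedes that consenters may differ and plans weights. But it does not say whether perceived risk is among the weighted outcomes, and weights that omit risk leave the bias almost unchanged.

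**Decliners' scores may be scarce.** This also stands. A reader might infer that 6.c discards a full set of decliners' scores; the documents do not show that. The change log calls secondary-outcome data in non-consenters extremely limited. Changes to Protocol 7.a reports early withdrawals from the BASC phone screen. Final Protocol 8.d.ii surveys only MOVE IT patients who want to learn more, so gaps may persist after April 2018. Those with a score are also a post-randomisation group, because the surveys follow the incentive announcement. This limits the gain, but it does not justify restricting further to consenters by default.

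**Conclusion.** The concern holds for the perceived-risk comparison in 6.c. The direction follows if incentives raise enrolment and perceived risk lowers it, or if the risk slope flattens with incentive. The size rests on the assumed slopes, enrolment rates and score shapes. It runs from nil (no risk-enrolment link), through 6-16% (BASC-like) and 5-8% (MOVE IT-like) false rejection under a common slope, to 36-43% and 24-25% under a flattening slope. In the last case the bias is neither modest nor confined to BASC.

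A reader might infer that the undue-inducement conclusion is compromised. The documents do not support that: the primary interaction model has enrolment as its outcome and is not limited to consenters, and the stopping rules use the same interactions. What does reach 5.c is a separate gap, since neither 5.c nor 6.b says whether the BASC phone or intake score is used. Nor can a direction of bias be claimed for the other secondary outcomes.

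**What to change.** 1. In 6.c, compare perceived risk by randomised arm in all randomised participants with a recorded pre-decision score. Keep the consenters-only result as a sensitivity analysis.
2. Report the number and percentage scored by arm and consent status.
3. State in both 5.c and 6.b which BASC administration is used. If intake is the 6.b outcome, analyse everyone who reached intake, not only signers, and also report the all-scored phone comparison, noting that the phone score precedes reading of the consent form.
4. State whether perceived risk is among the weighted outcomes. If so, include risk score by arm in the consent model and name its covariates.
5. State that residual selection remains, because the surveys follow the incentive announcement and some decliners have no score.

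The cost is SAP wording, an added analysis of a scale that the primary model already requires from decliners (plus an intake comparison in BASC if intake is the outcome), and one availability table. The gain is small if few decliners have a score, and the table will show whether that is so.
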